## VI. OUTCOMES (What is the anticipated actionable outcome?)

The study will provide novel insights into the incidence and consequences of COVID-19 associated myocardial injury in US population and its impact in early and late outcomes after the infection. We plan to develop a statistical model to predict the risks for myocardial injury induced death in COVID-19 patients and identify responses to different treatment strategies. This information will be pivotal for other centers who have yet had the surge of COVID cases. We

plan on fast track publication. Furthermore, electrocardiography, echocardiography and radiology data analyses will be used to uncover the potential mechanisms responsible for the link between myocardial injury and mortality. The findings will provide invaluable insights into the clinical outcomes and mechanisms underlying the collision between the acute COVID-19 epidemic and ongoing epidemic of cardiovascular disease.

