#### **III. STUDY POPULATION** (What population(s) is being studied?)

By October 2020, there had been 4,695 COVID-19 positive patients treated in the Mount Sinai Hospital (MSH). All consecutive patients admitted to the MSH system from February 2020 to October 2020 with laboratory-confirmed COVID-19 will be included in the retrospective study.

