## **IV. STUDY DESIGN AND PROCEDURES**

Medical history, demographic characteristics, clinical data (symptoms, treatment, complications and outcomes), laboratory findings and cardiac biomarkers on admission and during hospitalization will be collected retrospectively using electronic medical records by trained research personnel and reviewed by physicians. In addition, we will collect available electrocardiography, echocardiography and radiography (chest radiography or computed tomography) data. Patients will be categorized according to the presence or absence of cardiac injury defined as blood levels of high sensitivity troponin (hsTn) above the 99th-percentile upper reference limit. The primary end point will be death; secondary end points will include the rate of pulmonary embolism, acute kidney injury and admission to the intensive care. The study population will be stratified into categories according to the presence and type of myocardial injury according to the Fourth Universal Definition of Myocardial infarction. The cumulative incidence of all-cause mortality will be assessed using the Kaplan-Meier method and compared across the study groups with the log-rank test. Multivariate regression models will be used to determine the independent risk factors for death. Statistical analyses will be performed by an independent statistical center not involved in the data collection

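### The death-risk model has no validation or calibration step and a mislabelled outcome, so the plan cannot support its use at other centers

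*Combined protocol and SAP*

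**What the plan says.** - **The model.** Section VI (Outcomes): "We plan to develop a statistical model to predict the risks for myocardial injury induced death in COVID-19 patients". The same sentence adds responses to different treatments.
- **The intended audience.** The next sentence of Section VI: "This information will be pivotal for other centers who have yet had the surge of COVID cases".
- **The development data.** Section III (Study Population): "All consecutive patients admitted to the MSH system from February 2020 to October 2020 with laboratory-confirmed COVID-19 will be included in the retrospective study". The section counts 4,695 positive patients by October 2020. It describes no split by hospital or period.
- **The outcome.** Section IV (Study Design and Procedures) makes death the primary end point and says: "The cumulative incidence of all-cause mortality will be assessed using the Kaplan-Meier method". No cause-of-death adjudication is described.
- **The modelling method.** Section IV: "Multivariate regression models will be used to determine the independent risk factors for death". An independent statistical center will do the analysis.

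The available text mentions no resampling, held-out hospital or period, external data set, calibration measure, discrimination measure or model updating. The section numbers run from IV to VI, so this statement covers only the text that can be read.

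**The concern.** Two things do not fit together.

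First, a prediction model is promised and its value elsewhere is asserted, but the planned analyses are association analyses. A regression that identifies risk factors does not show whether predicted risks agree with observed risks in patients who did not contribute to the fit. An independent statistical center separates analysis from data collection, but it does not test a model. If only apparent performance is reported, a reader at another hospital cannot tell whether a predicted 20% means 20% there.

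Second, the predicted event is described as death caused by myocardial injury, while the event analysed is death from any cause. A model fitted to all-cause death predicts all-cause death, whatever it is called. An outside user would be misled about what the probability refers to.

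The primary mortality comparison between injury groups is not affected. At stake is the credibility of the result that Section VI presents as actionable.

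**Working it through.** The documents give no events count, model size or performance target, so there is no planned figure to reproduce. Three checks were made. Inputs marked (A) are assumptions.

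**1. Is overfitting the main problem?**

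Inputs: N = 4,695 (Section III); mortality m = 10–30% (A), which is 470 to 1,408 deaths; Nagelkerke R² f = 0.15–0.30 (A); p = 20 or 40 parameters (A).

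Formulas: expected shrinkage S = 1 − p/LR, with LR = −N ln(1 − R²), R² = f × [1 − exp(2L₀)] and L₀ = m ln m + (1 − m) ln(1 − m).

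- Low end (m = 0.10, f = 0.15, p = 20): R² = 0.15 × 0.478 = 0.0717, LR ≈ 349, S = 1 − 20/349 = 0.94.
- High end (m = 0.30, f = 0.30, p = 20): R² = 0.30 × 0.705 = 0.212, LR ≈ 1,116, S = 1 − 20/1,116 = 0.98.
- With p = 40 the range is 0.89 to 0.96.

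Overfitting is likely to be small to moderate. This is an inference from N; the plan does not check it.

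**2. What can a change of population do?**

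The Introduction cites two cohorts with in-hospital mortality of 59.6% and 51% with injury, and 8.9% and 4.5% without. Using one cohort's mortality to predict the other gives these observed/expected (O/E) ratios:

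| Group | First predicts second | Second predicts first |
|---|---|---|
| Without injury | 4.5/8.9 = 0.51 | 8.9/4.5 = 1.98 |
| With injury | 51/59.6 = 0.86 | 59.6/51 = 1.17 |
| All, 20% injured (A) | 13.80/19.04 = 0.72 | 19.04/13.80 = 1.38 |
| All, 40% injured (A) | 23.10/29.18 = 0.79 | 29.18/23.10 = 1.26 |

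For example, at 20% injured: 0.2 × 59.6 + 0.8 × 8.9 = 19.04% and 0.2 × 51 + 0.8 × 4.5 = 13.80%.

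A simulation separated the two kinds of error: a logistic model with 20 predictors, N = 4,695, mortality 15% or 25% (A) and 60 repeats. In new patients from the same population the calibration slope was 0.96–0.97 and O/E 1.00–1.01. With the same predictor effects but the odds of death halved in the target (A), O/E fell to 0.59–0.63. With the odds doubled (A), it rose to 1.47–1.61. A well-fitted model can therefore be well off in level, and a larger N does not change that.

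**3. Could the existing cohort reveal such a shift?**

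Formula: SE(ln O/E) = √[(1 − m)/deaths]; the 95% factor is exp(1.96 × SE).

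- Hold out 20% at m = 0.10 (A): 4,695 × 0.2 × 0.1 ≈ 94 deaths, SE = √(0.9/94) = 0.098, factor 1.21.
- Hold out 30% at m = 0.30 (A): 4,695 × 0.3 × 0.3 ≈ 423 deaths, SE = √(0.7/423) = 0.041, factor 1.08.
- A small set of 10% at m = 0.10 (A): 4,695 × 0.1 × 0.1 ≈ 47 deaths, SE = √(0.9/47) = 0.138, factor 1.31.

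With 94 or more deaths held out, a 25% discrepancy is detectable. With about 47 it is not.

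**The case against.** - **No tool is offered.** A reader might infer that a score is being released to other hospitals. Section VI does not say so. It speaks of information, which also covers treatment responses, and promises no calculator or threshold. That stands. But the model is named in the sentence just before, under a heading about actionable outcomes, so the claim of value elsewhere reaches it.
- **The model is peripheral.** The aim in Section II is incidence, outcomes and predictors of injury, and developing a model now and validating it externally later is legitimate. That also stands, and it limits the weight of the point. A development-only study should say that it is one, and should still report internal validation.
- **Changing mortality is not documented.** A reader might infer that mortality fell between February and October 2020, so that a pooled model over-predicts in later patients. With 60% early patients and mortality of 25% then 15%, expected/observed is (0.6 × 25 + 0.4 × 15)/15 = 1.40; with 90% early and 30% then 10%, it is (0.9 × 30 + 0.1 × 10)/10 = 2.80. Every input is assumed. The documents give no mortality for this hospital system, by month or overall, so they support neither the direction nor the size.
- **The last months may be the wrong test.** Centers still awaiting a surge may resemble this system's early months more than its late ones. The documents do not settle this, so holding out only the final months would be a weak choice.
- **By-hospital validation may not be feasible.** Section III refers both to one hospital and to a system, with no count of sites or deaths per site. This stands, and the fix is conditional on it. Hospitals within one system also test transport only in part.
- **The outcome label may be shorthand** for death among patients with injury. If so, the text should say that, because it changes the population in which the model is developed.

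**Conclusion.** The point holds as an omission and a mislabelled outcome. As written, the plan would yield apparent performance in one pooled hospital system, for an outcome that is all-cause death under another name. That cannot support the Section VI claim about other centers.

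If baseline mortality differs between hospitals or periods, the model could be materially miscalibrated whatever the cohort size. How large the error would be cannot be established: the documents give no mortality for this system by hospital or period. The two-fold gap between the cited cohorts shows how far centers can differ and is not a forecast. Part of it may be sampling error and case mix, and the denominators are not given. The simulated O/E of about 0.6 and 1.5–1.6 rests on assumed halving and doubling of the odds.

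The documents do not support the stronger conclusions that the model will be miscalibrated, or that it will over-predict in a particular direction. The outcome mismatch needs no numerical assumption. The weight is moderate: this should be corrected, but the primary mortality comparison does not depend on it.

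**What to change.** 1. In Section VI, name the predicted outcome as all-cause death, matching Section IV, and state the population in which the model is developed.
2. Report discrimination and calibration with bootstrap optimism correction, repeating every model-building step in each resample.
3. Prespecify internal-external validation by calendar period, leaving out each period in turn and not only the last. Do the same by hospital where the system's hospitals have enough deaths. In each held-out set report the calibration intercept or O/E, the calibration slope and the c-statistic, with confidence intervals.
4. Limit the Section VI claim: state that external validation or recalibration is needed before use at other centers, because held-out parts of the same system are only a partial test.

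The cost is some extra analysis of data already being collected, and somewhat less favourable reported performance. No new patients or variables are needed beyond admission date and site.
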